5.2 Subject Screening and Informed Consent

5.2.1 Subject Screening

Subjects admitted for a procedure must be screened for clinical trial eligibility by a member of the clinical trial/investigation team (physician and/or research coordinator) previously trained to the clinical trial Protocol, and if applicable will be entered into a site specific screening log.

Subjects meeting the general inclusion and exclusion criteria will be asked to sign and date an informed consent. These patients will then be entered into the screening log (as applicable, also the reason for screen failure as well as supporting data will be entered into the log).

Screening imaging will be used for the final assessment of subject eligibility. Subjects who do not satisfy echocardiographic inclusion and exclusion criteria (screen failure) will not undergo the TVRS procedure in this clinical trial/investigation. These subjects will be followed for 30 days after consent for adverse events, then withdrawn from the study.

Patient data will be collected following enrollment into the trial.

Screening of a subject for possible inclusion in the trial may commence once a subject has been identified as symptomatic, having moderate or greater grade tricuspid regurgitation. Subject's general medical

(Version 2.0; 01 February 2018)

eligibility must be assessed by the sites through subject's interview and subject's medical record review prior to the TVRS procedure and within the time windows stipulated (see **Table 2** for more details). Relevant standard of care tests performed prior to obtaining informed consent can be used to determine eligibility if those tests were within the screening time window. Signed and dated informed consent **must** be obtained prior to any test/evaluation that is not standard of care. Additionally, signed and dated informed consent is **required** prior to any transmission of patient data to the ECL or Sponsor.

Site Heart Team will evaluate the following assessments

- Subject meets all general and echocardiographic inclusion criteria
- Subject does not meet any of the general and echocardiographic exclusion criteria
- Subject is evaluated by the Site Heart Team to confirm that they are adequately treated per applicable standards, including treatment for coronary artery disease, right ventricular dysfunction, mitral regurgitation, tricuspid regurgitation, and heart failure. Subjects with current or prior symptoms of heart failure and reduced LVEF should be on stable optimally up-titrated medical therapy recommended according to current guidelines as standard of care for heart failure therapy in the United States and Europe. See 'APPENDIX II: Definitions' for definition of optimal therapy. Additionally, the Site Heart Team must confirm that the subject is appropriate for percutaneous transcatheter intervention.
- Clinical, physical, and labs exams must be performed:
 - Medical history
 - o Weight, temperature, blood pressure and heart rate
 - Modified Rankin Scale assessment
 - o Perform a pregnancy test, as appropriate
 - o Measure BNP or NT-proBNP level
 - Measure AST or ALT level
- If Site Heart Team deems this subject is at high risk for tricuspid valve surgery and an appropriate candidate for TVRS, their TEE and TTE images will be submitted to the independent ECL.
 - Site must review the TTE and TEE images and confirm that subject has TR and suitable tricuspid valve anatomic criteria, without intracardiac mass, thrombus or vegetation. Trained Abbott personnel may provide support to sites in reviewing TTE/TEE images.
- After the ECL has confirmed subject eligibility, sites will be notified by the Sponsor to compile and submit the following information for Eligibility Committee review:
 - Obtain and review Subject's medical records and history.
 - Complete a physical exam, including an assessment of subject's cardiac status and vital signs measures (e.g. height, weight, heart rate, blood pressure and temperature)
 - o Assess subject's NYHA Functional Class and Modified Rankin Scale
 - Have the subject examined by the investigator to assess optimization level of his/her medications, and appropriateness for TVRS.

(Version 2.0; 01 February 2018)

• If patient does not meet any of the screening requirements, then the subject is considered a screen failure.

5.2.2 Study Informed Consent

The Investigator or designee, who has been trained on the protocol, will explain the nature and scope of the trial, potential risks and benefits of participation, and answer questions for the subjects. All subjects, or their legally authorized representatives* (where allowed per local regulations), must sign and date the Institutional Review Board (IRB)/Ethics Committee (EC) approved informed consent form prior to any clinical trial/investigation-specific procedures. The ICF must also be signed by the investigator or designate (if allowed per country specific regulations). The completed ICF must be kept in the subject's medical records. The whole consenting process, date, and provisioning of a copy to the subject must be documented in the subject's medical records.

Subjects who belong in the Vulnerable Population (definition in **Appendix II**) will not be allowed into this trial.

For US subjects: In addition, an authorization for use and disclosure of the subject's protected health information, in accordance with the Health Insurance Portability and Accountability Act (HIPAA), must be obtained from the subject or their legally authorized representative.

5.2.3 Enrollment of Medicare Beneficiaries (US Cohort only)

Early use of the TVRS system indicates that patients that are candidates for the therapy are an older patient population typically managed under Medicare. Investigator-driven studies showed mean ages of 78 +/- 7 years (N=18, Braun et al)³⁰ and 76.6 +/- 10 years (N=64, Nickenig et al)³¹. It is expected that enrolled patients in the TRILUMINATE study will be within this age range, with the demographic characteristics and cardiovascular risk factors representative of the Medicare patient population as part of the overall cohort. These criteria are not expected to have a negative effect on the recruitment or retention of underrepresented populations. Section 15 describes how all enrolled subjects, including Medicare beneficiaries, may be affected by the device under investigation.

5.3 Subject Enrollment

Subjects are enrolled in the TRILUMINATE Trial upon signing and dating the informed consent form.

^{*} For Switzerland Only: A legally authorized representative will not be allowed to provide informed consent for a patient.

³⁰ Braun D, Nabauer M, Orban M, Orban M, Gross L, Englmaier A, Rösler D, Mehilli J, Bauer A, Hagl C, Massberg S, Hausleiter J. Transcatheter treatment of severe tricuspid regurgitation using the edge-to-edge repair technique. EuroIntervention, 2017 Feb 3:12(15):e1837-e1844.

³¹ Nickenig G, Kowalski M, Hausleiter J, Braun D, Schofer J, Yzeiraj E, Rudolph V, Friedrichs K, Maisano F, Taramasso M, Fam NP, Bianchi G, Bedogni F, Denti P, Alfieri O, Latib A, Colombo A, Hammerstingl C, Schueler R. Transcatheter Treatment of Severe Tricuspid Regurgitation with the Edge-to-Edge: MitraClip Technique. Circulation. 2017 Mar 23.

(Version 2.0; 01 February 2018)

5.4 Subject Discontinuation

Withdrawal:

Each enrolled subject shall remain in the trial until completion of the required follow-up period; however, a subject's participation in any clinical trial is voluntary and the subject has the right to withdraw at any time without penalty or loss of benefit. Conceivable reasons for discontinuation may include, but not be limited to, the following:

- Subject death
- Subject voluntary withdrawal
- · Subject withdrawal by physician as clinically-indicated
- Subject lost-to follow-up as described below

The Sponsor must be notified of the reason(s) for subject discontinuation. The site will provide this information to the Sponsor. Investigators must also report this to their respective IRB/EC as defined by their institution's procedure(s).

No additional follow-up will be required or data recorded from subjects once withdrawn from the trial, except for the status (deceased/alive).

However, if a subject withdraws from the study due to problems related to the investigational device safety or performance, the investigator shall ask for the subject's permission to follow his/her status/condition outside of the clinical investigation.

Lost-to-Follow-up:

If the subject misses two consecutive scheduled follow-up time points, and the attempts at contacting the subject detailed below are unsuccessful, then the subject is considered lost to follow-up. Site personnel shall make all reasonable efforts to locate and communicate with the subject (and document these efforts in the source documents), including the following, at each contact time point.

For all countries, except Switzerland:

- A minimum of 3 telephone calls over a period of 10 days to contact the subject or his/her relative/caregiver (where allowed per local regulations) should be recorded in the source documentation, including date, time, and name of site personnel trying to make contact.
- If these attempts are unsuccessful, a certified or registered letter with confirmed receipt should be sent to the subject. The registered letter will request the subject to contact the site.
- If the above attempts are unsuccessful, the patient's general practitioner shall be contacted to investigate about the subject's whereabouts and his/her health status (where allowed per local regulations).

For Switzerland Only:

• In the event that the 3 phone calls made over a 10-day period to reach the patient are unsuccessful, the patient's general practitioner shall be contacted regarding the patient's health status at the same time that the registered letter is sent to the subject. This modification

(Version 2.0; 01 February 2018)

corresponds to the quick measures for capturing the whereabouts and state of health of subjects by the Swiss Competent Authority and permitted by regional regulations.

• In case of a subject not being able to be located, the monitor will verify that adequate measures have been undertaken to contact the subject's treating General Practitioner and exchange data about the whereabouts and health status of the subject.

If a subject misses one or more non-consecutive follow-up contact time points, it will be considered a missed visit. The subject may then return for subsequent visits. If the subject misses two consecutive follow-up time points the subject will be considered lost-to-follow-up.

However, if a subject withdraws from the study due to problems related to the investigational device safety or performance, the investigator shall ask for the subject's permission to follow his/her status/condition outside of the clinical investigation.

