3.3 Follow-Up Compliance

The Sponsor will work with investigational sites to maintain a high follow-up compliance as follows:

- 1. Sponsor will emphasize to the site the importance of subject follow-up during site initiation visits and subsequent communications. Site should communicate the importance to each subject.
- 2. Sites will be informed to promptly reschedule any missed subject visits, and to reinforce the necessity of a follow-up visit.

[figure not shown]
²⁷ Zoghbi WA, Adams D, Bonow RO, Enriquez-Sarano M, Foster E, Grayburn PA, Hahn RT, Han Y, Hung J, Lang RM, Little SH, Shah DJ, Shernan S, Thavendiranathan P, Thomas JD, Weissman NJ. Recommendations for Noninvasive Evaluation of Native Valvular Regurgitation: A Report from the American Society of Echocardiography Developed in Collaboration with the Society for Cardiovascular Magnetic Resonance. J Am Soc Echocardiogr. 2017 Apr;30(4):303-371.

(Version 2.0; 01 February 2018)

- 3. Site is advised to involve Sponsor when needed. Example: Arrange alternate transportation if a scheduled visit is missed due transportation/travel issues, or due to subject illness
- 4. Sites should document reasons for any subject withdrawals from the trial, and request agreement for a follow-up call from the investigator at the end of the trial.
- 5. Sites should monitor follow-up rates closely to promptly identify and address any issues.

Additionally, investigational sites will be educated on the importance of maintaining low rates of withdrawals, and will be expected to make all effort to maintain low withdrawals during trial conduct. Withdrawals from the trial will require discussion between investigator and the Sponsor.

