1. CARDIOVASCULAR DEATH (VARC)

Per the Valve Academic Research Consortium (VARC)⁵ as any one of the following:

- Any death due to proximate cardiac cause (e.g. MI, cardiac tamponade, worsening heart failure)
- Unwitnessed death and death of unknown cause
- All procedure-related deaths, including those related to a complication of the procedure or treatment for a complication of the procedure
- Death caused by non-coronary vascular conditions such as cerebrovascular disease, pulmonary embolism, ruptured aortic aneurysm, dissecting aneurysm, or other vascular disease

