2.1.4 Survival Analyses

Survival analysis will be conducted to analyze time-to-event variables, e.g. all-cause mortality. For analyses of clinical events (e.g. MAE) beyond 30-day follow-up, Kaplan-Meier¹¹ estimate will be utilized.

Subjects without events will be censored at their last known event-free time point. Survival curves will be constructed using Kaplan-Meier estimates. Summary tables for endpoints will include failure rates (Kaplan-Meier estimates), and confidence interval for the failure rates.

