2.2.1.2 Primary Safety Endpoint Analyses

The primary analysis population for the primary safety endpoint is the PAP population. The MAE rate at 6 months will be calculated and tested against a pre-specified PG of 39%. The Kaplan-Meier analysis will be used to compute the MAE rate at 6 months; the standard error and confidence limits will be computed using Greenwood's method.

The same analysis as above may be performed for the PTE population.

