2.6 Multiplicity Issues

the overall Type I error rate of the study is conservatively controlled at 2.5% and there is no need to adjust the level of significance for multiplicity.

All analyses will be performed using SAS®¹³ for Windows, version 9.2 or higher.

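### Non-fatal major adverse events after withdrawal are not recorded, so leavers are censored, possibly informatively, in the 6-month primary safety test

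*Protocol*

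**What the plan says.** Protocol 5.4 (Subject Discontinuation) lists voluntary withdrawal and withdrawal by the physician on clinical grounds among the reasons for leaving. It then says: "No additional follow-up will be required or data recorded from subjects once withdrawn from the trial, except for the status (deceased/alive"). For a subject who leaves because of device safety or performance, "the investigator shall ask for the subject's permission to follow his/her status/condition outside of the clinical investigation".

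Protocol 4.2 defines the MAE composite as cardiovascular death, MI, stroke, new onset renal failure, endocarditis requiring surgery, and non-elective cardiovascular surgery for a device-related event. SAP 2.2.1.2 states "The MAE rate at 6 months will be calculated and tested against a pre-specified PG of 39"%, and "The Kaplan-Meier analysis will be used to compute the MAE rate at 6 months; the standard error and confidence limits will be computed using Greenwood's" variance formula. SAP 2.1.4 adds: "Subjects without events will be censored at their last known event-free time point".

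SAP 2.4 excludes missing data from the main analyses. It plans a tipping-point analysis of the 6-month safety endpoint over the whole primary analysis population.

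Two other places bear on this. Protocol 7.3.1 has all adverse events collected on every subject to the 3-year visit, with no exception for withdrawal. Protocol 3.3 tells sites, when a subject withdraws, to "request agreement for a follow-up call from the investigator at the end of the trial".

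**The concern.** The device is a one-time implant, so leaving the study does not end exposure to it. The protocol accepts this elsewhere: follow-up continues when no clip was implanted (6.5), after valve surgery (6.9) and after explant at surgery (6.10). Withdrawal is the exception.

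After withdrawal, MI, stroke, renal failure, endocarditis surgery and device-related surgery have no route into the trial data. For a consenting subject who left over a device problem, the site may know of such an event while the database cannot hold it. Censoring then gives the leaver the same future risk as those who stayed. If leavers are at higher risk, the Kaplan-Meier MAE rate is too low, and the test against 39% is easier to pass than its nominal error rate implies.

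**Working it through.** **Inputs.** n = 85 analysis subjects (Protocol 5.7), with leavers not replaced (5.9). Performance goal 39%, Kaplan-Meier with Greenwood standard error (SAP 2.2.1.2). SAP 2.6 says "the overall Type I error rate of the study is conservatively controlled at 2.5"%. The 97.5% one-sided limit is stated only for effectiveness, so applying it to safety is an assumption. The readable text does not say whether the Greenwood limit is linear or transformed, so both are shown. Withdrawal rates and leaver risks are assumptions throughout. The expected MAE rate and power are not readable, so the sample size cannot be reproduced.

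**1. Decision boundary, nobody censored.** The linear Greenwood limit is p + 1.96·√(p(1−p)/n).
- 24/85: 0.282 + 1.96 × 0.0488 = 0.378, pass.
- 25/85: 0.294 + 1.96 × 0.0494 = 0.391, fail.

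The log-log limit is 1 − S^exp(1.96·SE/(S·|ln S|)), with S = 1 − p.
- 23/85: 0.378, pass.
- 24/85: S = 0.718, SE = 0.0488, giving 0.391, fail.

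The exact binomial limit also passes at 23 (0.378) and fails at 24 (0.390). The largest passing count is therefore 24 (linear) or 23 (log-log or exact). True type I error at 39% is 0.0254 or 0.0144 respectively.

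**2. Losing one or two events just after the procedure.** Each lost event leaves both numerator and denominator.

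| True events | Lost | Analysed | Linear limit | Log-log limit |
|---|---|---|---|---|
| 24/85 | 1 | 23/84 | 37.8% → 36.9% (pass, pass) | 39.1% → 38.3% (fail, pass) |
| 25/85 | 1 | 24/84 | 39.1% → 38.2% (fail, pass) | 40.3% → 39.5% (fail, fail) |
| 26/85 | 2 | 24/83 | 40.4% → 38.7% (fail, pass) | 41.6% → 40.0% (fail, fail) |

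Under log-log the sensitive zone sits one event lower; it does not disappear.

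**3. Distance from the boundary (linear).** A pass becomes a fail once observed plus hidden events reach 25, so the hidden MAEs needed are 25 minus the observed count: 17 with 8 observed, 12 with 13, 8 with 17, 4 with 21, 2 with 23.

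Worst cases, with about half the observed events before a common withdrawal time:
- 4 leavers, 21 observed events: S = (75/85) × (60/71) = 0.746, rate 25.4%, limit 34.9%, pass. If all 4 had an MAE: 25/85, limit 39.1%, fail.
- 9 leavers, 17 observed: rate 21.4%, limit 30.5%, pass. If all 9 had one: 26/85, limit 40.4%, fail.
- 9 leavers, 8 observed: limit 16.6%, pass. If all 9 had one: 17/85, limit 28.5%, still pass.

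**4. Effect on the error rate.** Simulation of 20,000 trials per setting: true 6-month MAE rate 39%, withdrawals uniform over 6 months, linear limit, leaver hazard after withdrawal a multiple of the stayers'. Chance of passing (2.5% with no withdrawals):

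| Withdrawing | ×1 | ×2 | ×3 | ×5 |
|---|---|---|---|---|
| 5% | 3.2% | 4.2% | 5.3% | 6.3% |
| 10% | 3.2% | 5.1% | 7.5% | 11.4% |
| 20% | 3.4% | 8.0% | 13.9% | 26.5% |

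The ×1 column is not due to informative withdrawal; the rise to its right is. With 10% withdrawing, the mean Kaplan-Meier estimate is 37.8% at ×2 and 35.6% at ×5, which is 1.2 and 3.4 points below the true 39%. For each setting these are upper bounds, because the simulation also hides deaths, which the protocol keeps.

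**The case against.** The strongest reply is that the gap is narrow and the SAP already plans for it. An MAE that prompts withdrawal precedes it and counts. Valve surgery, a likely consequence of a serious device complication, does not end follow-up. Protocol 3.3 requires withdrawals to be discussed with the sponsor and kept low. The tipping-point analysis would expose a result that one or two missing outcomes could reverse. Subjects also have a right to leave, and asking separately about later follow-up respects it. All of this stands and limits the size of the problem. It does not make the primary estimate correct, and it does not explain why an event known to the site in a consenting subject should stay out of the data.

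A reader might infer more than the documents support:
- That MAEs in device-problem leavers never reach the test. Only non-fatal events after withdrawal are lost.
- That leavers are the highest-risk subjects. This is plausible for device-problem withdrawals, but no withdrawal rate or leaver risk is given.
- That deaths recorded without a cause lower the MAE rate. Appendix II classes "Unwitnessed death and death of unknown cause" as cardiovascular, so a counted death of unknown cause would raise it. What the readable SAP text leaves open is whether a death found after withdrawal is counted or the subject stays censored.
- That the end-of-trial call in 3.3 contradicts 5.4. It may simply be how vital status is obtained.

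The analysis-population section is not readable in the public copy, so nothing is concluded about how that population treats leavers.

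**Conclusion.** The point holds in a limited form. Non-fatal MAE components after withdrawal and before 6 months are not collected, and those subjects are censored in the primary safety test, possibly informatively. Only the tipping-point analysis addresses this, and it leaves the primary estimate as it is.

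The verdict is at risk mainly near the boundary, about 23 to 25 events of 85 depending on the limit used, or if withdrawals are many. At 8 observed events it would take 17 hidden MAEs to reverse a pass. The error-rate figures rest on assumed withdrawal rates of 5% to 20%, assumed hazard ratios and a linear limit, so they show the direction and possible range rather than a forecast. A claim that the primary conclusion is probably wrong would not be supported.

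Separately, 5.4 and 7.3.1 give incompatible instructions for adverse events in withdrawn subjects and must be reconciled. This is a cheap improvement, not a fatal flaw.

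**What to change.** In Protocol 5.4, make withdrawal stepwise. At withdrawal, ask whether phone or record follow-up may continue. For those who agree, including device-problem leavers and physician withdrawals, record MAE components and the date and cause of death in the eCRF through at least 6 months, send them to the Clinical Events Committee, and include them in the primary safety analysis. Subjects who refuse stay censored, and the tipping-point analysis continues to cover them. Align 7.3.1 with the revised text.

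In the SAP, state how a death found after withdrawal enters the Kaplan-Meier analysis.

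Cost: protocol and consent wording, one eCRF page, a few extra contacts or record checks, and possibly a slightly higher observed MAE rate.

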5.9 Trial Completion

A Trial Completion eCRF must be completed for each patient when:

- the subject is considered lost to follow-up per the above definition or
- the subject withdraws from the Trial or
- the subject is withdrawn due to screen failure or
- the investigator withdraws the subject from the trial or
- the subject dies or
- the subject completes the Trial (e.g., 3 year follow-up time point has been reached) or
- the sponsor terminates the Trial.

Sponsor must be notified of the reason for subject discontinuation. The site will provide this information on the eCRF. Investigators must also report this to their EC/IRB as defined by their institution's procedure. Subjects will not be replaced.

(Version 2.0; 01 February 2018)

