1.3 Trial Design

The TRILUMINATE Trial is a prospective, single arm, multi-center study of the TVRS for treating symptomatic moderate or greater TR in patients currently on medical management and who are deemed high-risk for tricuspid valve surgery and appropriate for percutaneous transcatheter intervention.

A minimum of 85 subjects will be prospectively enrolled and undergo the TVRS procedure in up to 25 sites, in Europe, Canada and the United States:

• A clinical report will be included as part of the submission for CE Mark and other regulatory submissions, as appropriate.

All subjects will have scheduled office visit evaluations at baseline, discharge, 30 days, 6 months, 1 year, 2 years, and 3 years.

The US subjects enrolled into the TRILUMINATE Protocol (#16-517) will receive additional follow-up assessments at 4 years (\pm 28-days) and 5 years (\pm 28-days) post-procedure. The subject may perform the follow-up with a phone interview with the investigational site, or with visits as deemed clinically warranted by the site investigator.

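### Protocol Section 5.4 defines loss to follow-up twice; the second version omits the failed-contact condition, so read literally it closes out a reachable subject who misses two consecutive visits

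*Protocol*

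**What the plan says.** Protocol Section 5.4 states the rule at two places.

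- **Fuller rule**, opening the lost-to-follow-up text: "If the subject misses two consecutive scheduled follow-up time points, and the attempts at contacting the subject detailed below are unsuccessful", and only then is the subject lost. The attempts are three telephone calls over ten days, a registered or certified letter, and the general practitioner. In Switzerland the letter and the general practitioner contact run in parallel. Efforts are required at each contact time point.
- **Shorter rule**, after the country-specific steps: "If the subject misses two consecutive follow-up time points the subject will be considered lost-to-follow-up". The sentences just before it read: "If a subject misses one or more non-consecutive follow-up contact time points, it will be considered a missed visit. The subject may then return" for later visits. Return is stated only for non-consecutive misses.

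Three other places bear on the consequence.

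- Section 5.9 requires a Trial Completion eCRF when "the subject is considered lost to follow-up per the above definition or" any other listed trigger applies. It speaks of one definition.
- Under its withdrawal heading, Section 5.4 lists "Subject lost-to follow-up as described below" among the reasons for discontinuation. It then says that a withdrawn subject contributes no further data apart from whether he or she is alive. Section 7.3.1 has adverse events collected on every subject up to the 3-year visit.
- SAP Section 2.1.4: "Subjects without events will be censored at their last known event-free time point".

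**The concern.** The two rules treat the same subject differently. Take someone too frail to travel who misses two visits in a row but answers the telephone. Under the fuller rule the condition "and the attempts at contacting the subject detailed below are unsuccessful, then the subject is considered lost to follow-up" is not met, so the subject stays in the trial. Under the shorter rule the subject is lost and a Trial Completion eCRF is due. With up to 25 sites, both readings could be applied in good faith.

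What is at stake is avoidable censoring. The MAE composite contains non-fatal events (stroke, MI, new onset renal failure, endocarditis requiring surgery, non-elective surgery for a device-related event) and cardiovascular death. A bare alive-or-dead check captures none of the non-fatal events and does not give the cause of death that the mortality component needs. If those who miss visits have a higher risk, the censoring is informative. The tipping-point analysis in SAP Section 2.4 covers only the 30-day effectiveness and 6-month safety endpoints, so the later results have no such check.

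**Working it through.** The plan gives no figure to reproduce: the readable text states no expected loss rate. The check is a comparison of texts, then an enumeration on the visit schedule, then an illustration of scale.

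**1. The two rules side by side**

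| | Two consecutive misses | Failed contact | Reachable subject with two misses |
|---|---|---|---|
| Fuller rule (5.4) | required | required | stays in |
| Shorter rule (5.4) | required | not mentioned | lost |

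Section 5.9 does not say which row applies.

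**2. What is collected afterwards**

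- If the data stop for withdrawn subjects in Section 5.4 reaches subjects labelled lost, its vital-status exception reaches them too. Non-fatal MAEs and cause of death are then not collected.
- If it does not reach them, Section 7.3.1 governs and adverse events are still due through 3 years.

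The Protocol does not choose between these.

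**3. When the shorter rule can bite** (schedule from Protocol Section 1.2)

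| Missed pair | Rule met at | Visits still to come | Results exposed |
|---|---|---|---|
| Discharge + 30 days | 30 days | 6 months, 1, 2, 3 years | 6-month primary safety and all later results |
| 30 days + 6 months | 6 months | 1, 2, 3 years | later results; the 6-month estimate only if no event status was obtained |
| 6 months + 1 year | 1 year | 2, 3 years | 1- to 3-year results |
| 1 year + 2 years | 2 years | 3 years | 2- and 3-year results |
| 2 years + 3 years | 3 years | none | little, as no later visit is lost |

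Only the first pair closes a subject before 6 months. The second pair matters for the primary endpoint because SAP Section 2.1.4 censors at the last known event-free time, not at close-out. Without an interim contact, that time could lie near discharge.

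**4. Scale, under assumptions only**

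Let k of 85 subjects be closed out event-free at one time point, with later MAE risk q_c, against q_r in those retained. Assume no other censoring.

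- Expected MAEs not recorded: k × q_c. For k = 1 to 8 (1.2% to 9.4% of 85) and q_c = 10% to 40%, this runs from 1 × 0.10 = 0.1 to 8 × 0.40 = 3.2.
- Kaplan-Meier gives the closed-out subjects the risk of the retained ones, so its shortfall is (k/85) × (q_c − q_r). With q_c = q_r it is zero. With k = 1 and a difference of 0.20 − 0.10 it is 0.10/85 = 0.12 percentage points. With k = 8 and a difference of 0.40 − 0.10 it is 8 × 0.30/85 = 2.8 percentage points.

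None of these values of k, q_c or q_r comes from the documents. The formula shows that a bias needs a difference in risk as well as lost subjects.

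**The case against.** The strongest reply is that the shorter sentence is shorthand. The subsection opens with the full definition and the contact procedure; the later sentence only contrasts consecutive with non-consecutive misses; and Section 5.9 refers to one definition. Protocol Section 3.3 also tells sites to reschedule missed visits promptly, to involve the sponsor over transport or illness, and to discuss withdrawals with the sponsor. A reachable subject should seldom be closed out in practice. This reading is possible. But the sentence stands as a complete rule that sorts subjects by visit pattern alone, and nothing says that the contact condition still applies.

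Three stronger readings are tempting and are not supported.

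- A reader might infer that deaths after close-out go unrecorded, or that the site has no further reporting duty. Section 5.4 keeps alive-or-dead status after withdrawal, and Section 7.3.1 points to continued adverse event collection. On neither reading of the data stop are deaths clearly lost.
- A reader might turn the 1-year survival figures in Section 15.1 (65% with severe TR, 90% without) into a count of missing deaths. That count would need an assumed number of closed-out subjects and would ignore the vital-status provision. It would also apply one population figure with no difference in risk, so it would show no Kaplan-Meier bias.
- A reader might infer that the 6-month primary safety result is seriously exposed. Only two visit pairs reach it, one of them conditionally. Contact is required at each time point, and the tipping-point analysis covers that endpoint.

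One limit also stands. A figure is missing beside the missed-visit text in Section 3.3, and Section 6.6 appears in the contents but has no heading in the readable body. It cannot be claimed that no telephone procedure exists.

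**Conclusion.** Wrong as written: an internal contradiction within Section 5.4, carried into Section 5.9. That the two rules differ is certain. Closing out a reachable subject follows only if a site applies the shorter rule alone. What could then be lost is later non-fatal MAEs and cause of death, because the Protocol does not say whether Section 5.4 or Section 7.3.1 governs.

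The exposure is mainly in the 1- to 3-year MAE estimates, which are secondary and descriptive (SAP Section 2.2.2). They are biased low only if subjects who miss visits are at higher risk, which is plausible here but is an assumption. Exposure of the 6-month primary safety estimate is limited to the two pairs identified above. The size cannot be stated from the documents, and the illustration gives scale only.

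**What to change.** - In Section 5.4, add to the shorter sentence the condition that the contact attempts described above have failed, or delete the sentence. Point Section 5.9 to that single definition.
- State that a subject reached by telephone has a missed visit and stays in the trial. Adverse events including MAEs, hospitalisations, vital status and cause of death are then collected by telephone. The SAP already accepts this mode for US subjects at years 4 and 5: "The subject may perform the follow-up with a phone interview with the investigational site".
- State that the alive-or-dead check also applies to subjects who are truly lost.

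The cost is a short amendment and a few telephone contacts. Event rates may look slightly less favourable because more events are captured.
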